8. CORRELATIVE/SPECIAL STUDIES

8.1 Laboratory Correlative Studies

Pre-treatment and post-treatment skin punch biopsies will be performed by PI. All research samples (blood and tissue) will be coded with the study participant identifier, and are collected by research team members. Experimental processing will be performed in PI's research lab in CCSR.

8.1.1 The histologic analysis will be performed by means of immunohistochemistry (IHC) and hematoxylin and eosin (H&E) staining of pre and post treatment biopsied tissue will be undertaken. Participants in this study will be consented for skin punch biopsies of the affected arm prior to treatment as well as post treatment (optional for control group). Two 6 mm full-thickness skin punch biopsy specimens will be obtained from the medial aspect of the forearm of affected limb, with an Acu-Punch (Fort Lauderdale, FL) disposable device. Biopsy

specimens will be immediately placed in formalin. Following biopsy, the skin edges will be sutured with a single butterfly suture, and the participant will receive a prophylactic antibiotic regimen of cephalexin 250 mg, 4 times daily for 2 days, or an equivalent regimen (if allergic to cephalexin). Skin punch biopsy will be performed at baseline and at completion (12 months post-treatment).

Paraffin-embedded tissue sections will be stained with hematoxylin-eosin (H&E, Richard-Allan Scientific, USA), goat polyclonal anti-LYVE-1 antibody (1:200, Santa Cruz Biotechnology, USA), 5-LO (Cell Signaling 3289), macrophage (Agilent Dako KP1), or neutrophil (anti-Myeloperoxidase antibody, Ab9535 Abcam); cutaneous lymphatic microvascular area will be quantitated through immunohistochemical staining of podoplanin with anti-D2-40 antibody (Dako IS072). Tissue samples will be sliced in 10 μ m-thick sections, and evaluated microscopically.

The impact of treatment on cutaneous histopathology will be evaluated through the use of an empirically-derived scoring system (comprised of dermal thickness, intercellular mucin content, deep dermal collagen content, and perivascular infiltrate); this quantitative assessment was developed by a dermatopathologist. The scoring of the specimens for this study will be performed by a blinded observer. Each characteristic will be weighted equally and each specimen will be assigned a cumulative subscale score (0 to 5) will be summed for a total score (0 to 20); higher scores indicate a greater degree of pathology. A quantitatively higher negative change will indicate a more favorable histological therapeutic response.

8.1.2 Luminex Bead Assays. Blood will be drawn in standard fashion, centrifuged for 10 minutes in 4°C room (CCSR 3112), plasma divided into microfuge tubes, and frozen at -80°C for biomarker analysis.

Custom human 62-plex kits (Affymetrix, Santa Clara, CA) will be utilized according to the manufacturer's recommendations with modifications as described below. Plasma samples will be mixed with antibody-linked polystyrene beads on 96-well filter-bottom plates and incubated at room temperature for 2 hours followed by overnight incubation at 4°C. Plates are vacuum-filtered and washed twice with PBS+0.2% Tween-20, followed by incubation with biotinylated detection antibody for 2 hours at room temperature. Samples are filtered and washed twice as above and re-suspended in streptavidin-PE. After incubation for 40 minutes at room temperature, 2 additional vacuum washes are performed, and the samples are re-suspended in Reading Buffer. Each sample will be measured in duplicate. Plates will be read using a Luminex 200 instrument with a lower bound of 100 beads per sample per analyte.

8.1.3 RNA analysis. Tissue from the skin biopsies may be homogenated in a laboratory blender. These samples will be stored frozen at -80° C, and later analyzed for total RNA content; integrity, up- and down-regulation analysis; and possibly other tests, except the RNA samples will not be used for sequencing analyses.

9. STUDY CALENDAR

	Pre-Study	S1	S2	S3	Surgery: VLNT with BioBridge (BB) Or VLNT only	T1 Mo. 3	T2 Mo. 6	T3 Mo. 9	T4 Mo. 12	T5 D-10 FU	T6 2-yr FU (BB group Only)	T7 3-yr FU (BB group Only)
Investigational Device (BioBridge Matrix)					X	X	X	X	X	X	X	X
Informed consent	X											
Demographics	X											
Medical history	X											
Concurrent meds	X	X	X	X		X	X	X	X	X	X	X
Physical exam	X	X		X		X	X	X	X	X	X	X
Vital signs	X	X	X	X		X	X	X	X	X	X	X
Height	X											
Weight	X	X	X	X		X	X	X	X	X	X	X
Performance status (ECOG)	X	X				X	X	X	X	X	X	X
CBC w/diff, platelets	X											
Serum chemistry	X											
EKG (as indicated)	X											
Adverse event evaluation		X	X	X		X	X	X	X	X	X	X
Measurements (BIS, VM, calipers)		X	X	X		X	X	X	X	X		
LymQoL survey		X	X			X	X	X	X	X		
Skin punch biopsy (optional for control group)			X						X			
Research labs			X						X			
Radiologic evaluation (Lymphoscintigraphy)				X						X *		
Pregnancy test (as indicated)												

* BioBridge Matrix recipients only.

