4. TREATMENT PLAN

Pre-op procedure:

- LSG baseline (it may be the same as one performed for research purposes)
- Venous duplex to evaluate the superficial and deep venous systems for clots and valvular insufficiency
- ICG fluorescence lymphatic mapping to assess the superficial lymphatic system
- Labs: CBC, CMP, PT/PTT, EKG, CXR
- Research samples: blood and skin samples; optional for control group
- Baseline photograph of limbs

Post-op:

- LSG at 12 months (it may be the same as one performed for research purposes)
- ICG fluorescence lymphatic mapping at 12 months

- Research samples: blood and skin samples; skin biopsies are optional for control group
- Photograph at 12 months

Time of procedure:

Operating time ~6 hours, additional 45 min for BioBridge placement; anesthesia ~10 to 12 hours, positioning, IV and arterial line placement, OR, etc (time is variable).

Description of procedure:

On the day of surgery, the patient will be sent to radiology for injection of Technecium-99 in the second web space of bilateral feet or contralateral arm in preparation for intraoperative lymph node transfer. Patient will be marked in the preoperative area. Patient will then be taken to the operating room, placed on the operating room table in the supine position with both arms abducted. Perioperative antibiotic will be given on-call to the OR. After general endotracheal anesthesia is established, the entire anterior chest, abdomen, proximal thighs and arm(s) will be prepped and draped in the usual sterile fashion. A surgical pause is taken to identify the patient and the procedure(s) to be performed.

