VLNT, 2 groups; one with BioBridge scaffold (intervention group), one VLNT only (control group), will occur between S3 and T1 visits.

T1 (3 months following surgery): physical exam, measurements, LymQoL survey, medication and symptom/AE review, VS, weight.

T2 (6 months following surgery): physical exam, measurements, LymQoL survey, medication and symptom/AE review, VS, weight

T3 (9 months following surgery): physical exam, measurements, LymQoL survey, medication and symptom/AE review, VS, weight.

T4 (12 months following surgery): physical exam, measurements, LymQoL survey, medication and symptom/AE review, VS, weight, skin punch biopsy (optional for control group), research labs. No compression garment wear x 10 days.

T5 (10 days after T4 visit): measurements, LymQoL survey, medication and symptom/AE review, VS, weight, stitch removal, LSG

T6 (2 years following surgery, BioBridge participants/intervention group): physical exam, medication and symptom/AE review, VS, weight.

T7 (3 years following surgery, BioBridge participants/intervention group): physical exam, medication and symptom/AE review, VS, weight.

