4.1 General Concomitant Medication and Supportive Care Guidelines

For VLNT, the following is routinely used pre-operatively (standard of care, SOC):

Chlorhexidine gluconate scrub.

Anesthesia risks (anesthesia and intubation) (SOC for VLNT placement; research for BioBridge placement):

Intubation injury; aspiration; anesthesia awareness; difficulty breathing after surgery; malignant hyperthermia; reaction to anesthesia drugs; nausea; vomiting; dry mouth; sore throat; shivering; sleepiness; confusion; hoarseness.

For VLNT, the following medications are routinely used intra-operatively (SOC for VLNT placement; research for BioBridge placement):

Midazolam; fentanyl; lidocaine; propofol; rocuronium; dexamethasone; ketamine; hydromorphone; acetaminophen; ondansetron; antibiotic (usually cephalexin unless allergic); scopolamine; magnesium; IV fluids (saline, lactated ringers).

Arterial line risks (SOC): Bleeding; hematoma; thrombosis; infection.

Rare risks: permanent arterial occlusion; pseudoaneurysm, sepsis.

Surgical risks (SOC for VLNT placement; research for BioBridge placement):

Bleeding; deep vein thrombosis (DVT); delayed healing; death; infection; injury during surgery; medical complications (pneumonia; MI; CVA; itching; scarring; numbness; neurovascular injury; tingling around surgical site(s); pain; persistent edema; seroma; flaps loss; donor site lymphedema; bruising; and need for reoperation.

For VLNT, the following medications are routinely used post-operatively (SOC):

Oxycodone; aspirin; ondansetron; Bacitracin zinc ointment; Lovenox; hydromorphone; heparin infusion

Lymphoscintigraphy (SOC for VLNT placement; research for BioBridge placement):

LSG will be performed for both research purposes and standard of care (1-2 scans pre-surgery and 1 to 2 scans 12 months post-surgery).

Lymphoscintigraphy requires four injections of 250uCi Sulfur Colloid, is performed at baseline and 12 months after surgery, and involves exposure to radiation. The LSG for research are not necessary for medical care. The additional amount of radiation exposure is about 7 mSv, which is approximately equal to 14% of the limit that radiation workers (for example, a hospital X-ray

technician) are allowed to receive in 1 year. This amount of radiation involves minimal risk and is necessary to obtain the research information desired.

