10.3.2.4 Measurement Time Points

LSG will be performed at baseline and 12 months post procedure

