10.3.2.5 Response Review

LSG will be evaluated by the co-investigator, [name], MD, Chief of Nuclear Medicine, who will be blinded the subjects' treatment status.

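### The calendar limits the Month 12 lymphoscintigraphy to BioBridge recipients while other sections set no arm limit; if it is followed, this exploratory endpoint has no scheduled Month 12 control research scan and its masked reading fails

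*Combined protocol and SAP*

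**What the plan says.** Section 9 (Study Calendar) schedules lymphoscintigraphy (LSG) twice: at S3 with no restriction, and at T5 with an asterisk that reads "BioBridge Matrix recipients only".

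Other places give the later scan without naming an arm:

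- Section 4, Post-op list: "LSG at 12 months (it may be the same as one performed for research purposes").
- Section 4, Study Visits: "T5 (10 days after T4 visit): measurements, LymQoL survey, medication and symptom/AE review, VS, weight, stitch removal, LSG".
- Section 10.3.2.4: "LSG will be performed at baseline and 12 months post procedure".
- Section 1.3 states the exploratory objective as serial LSG at enrollment and 12 months, again for no particular arm.

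Section 10.3.2.1 sets the endpoint population as participants with unilateral arm lymphedema who plan to have VLNT, which covers both arms. In section 10.3.2.5 the reader is a co-investigator "who will be blinded the subjects" (to treatment status).

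Section 4.1 classifies the scan as "Lymphoscintigraphy (SOC for VLNT placement; research for BioBridge placement") and adds "LSG will be performed for both research purposes and standard of care (1-2 scans pre-surgery and 1 to 2 scans 12 months post-surgery").

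**The concern.** The calendar and the endpoint sections describe different studies of lymphatic function. In one, both arms are scanned before and after surgery and read masked. In the other, only the device arm has a later research scan.

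The difference matters because the rationale in sections 2.2 and 2.3 is that the scaffold helps the transferred node connect to lymphatic vessels. Section 10.3.2.2 defines this endpoint partly as uptake in that node, and no other listed endpoint measures it. The plan also expects VLNT alone to work: section 4.1 reports an average volume reduction of 55 to 65%, and section 12.6.2 uses 51% for standard care. Improvement on the later scan is therefore plausible without the scaffold, and only a concurrent control change can show the difference. A scan missed at Month 12 cannot be recovered afterwards.

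**Working it through.** **Is the silence on arm elsewhere just shorthand for BioBridge only?** The protocol usually names an arm restriction where it intends one. In the same visit list, the next entry after T5 reads "T6 (2 years following surgery, BioBridge participants/intervention group"), and T7 is labelled likewise. Skin biopsy is repeatedly marked as optional for controls. Section 10.3.4 says that its histology endpoint concerns the intervention group; section 10.3.2 says nothing of the kind for LSG.

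**Scheduled Month 12 research scans** (48 and 12 from the synopsis and section 12.6.2, before dropout):

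| Source followed | BioBridge | Control |
|---|---|---|
| Calendar, section 9 | 48 | 0 |
| Sections 1.3, 4 and 10.3.2.4 | 48 | 12 |

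**Consequence for estimation.** The between-arm contrast is D = mean(Month 12 − baseline, BioBridge) − mean(Month 12 − baseline, control). Its standard error is SD × √(1/n_control + 1/n_BioBridge). With n_control = 0 the second mean does not exist and D cannot be estimated. The S3 scan in controls gives a baseline value but no change. What remains is the BioBridge change, which is the VLNT effect plus the scaffold effect plus any drift over time: one observed mean for several unknowns.

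**Consequence for masking.** If all 48 Month 12 research scans come from one arm and none from the other, a reader who knows the schedule knows the arm of every later scan.

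**What the both-arm version would buy.** The documents give no figure for LSG, so there is none to reproduce. As background, the primary figure does reproduce:

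- √(1/12 + 1/48) = 0.3227, so the standard error is 19 × 0.3227 = 6.13.
- At two-sided 0.05 (sidedness is not stated; assumed) and 90% power, the detectable difference is 6.13 × (1.960 + 1.282) = 19.9, against the stated 20%.
- Power at 20% is 0.903 by the normal approximation and 0.894 by the noncentral t.

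The same arithmetic in SD units for an LSG change score gives 0.3227 × (1.960 + 0.842) = 0.90 SD at 80% power, and 0.3227 × 3.242 = 1.05 SD at 90% (0.92 and 1.06 by the noncentral t). No LSG standard deviation is given, so this cannot be put in LSG units. Twelve controls would allow a comparison, but one sensitive only to large differences.

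**The case against.** The best defence is that the footnote marks only which scan is research. Section 4.1 calls LSG standard care for VLNT and research for BioBridge, and section 4 lets one 12-month scan serve both purposes, so controls could still be scanned clinically. This stands in part. A reader might infer that controls would have no LSG data, or no 12-month scan at all. The documents do not support either: controls keep the S3 scan, and a standard-care scan at 12 months is described. But no section says that the footnote has this meaning, that control clinical scans are collected for the endpoint, that they follow the same ten days without compression as T5, or that they reach the blinded reader.

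Second, the plan never explicitly promises a between-arm LSG comparison. Section 10.3.2 lacks the relative-to-control wording that 10.3.3 has for L-Dex, the opening of section 10 promises comparison for primary and secondary analyses, and the LSG paragraph in 12.5.2 has no comparative wording. This is correct. The comparison is implied by the all-VLNT population and the blinded reading, and the second of these is weak evidence alone, since 10.3.4 also has a blinded reader for an endpoint described in the intervention group.

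Third, silence in section 4 is imperfect evidence: T5 lists stitch removal without qualification although biopsy is optional for controls. A specific footnote may qualify general text, and no section says which governs.

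Fourth, a reader might infer that the LSG reader is in fact unblinded, or that LSG is the only test of the mechanism. Section 10.3.2.5 states blinding; its failure is a consequence of following the calendar, not something the plan declares. ICG mapping is also done at 12 months, although it is not a named endpoint, and histology examines lymphatic vessels in skin.

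**Conclusion.** The contradiction is real and should be resolved before any participant reaches Month 12. If the calendar is what sites carry out, scheduled Month 12 research scans are 48 BioBridge and 0 of 12 control. No control research change score exists, the endpoint cannot distinguish the scaffold from VLNT alone, and the promised masking fails for the later scans.

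This rests on two conditions that the documents leave open: that the calendar prevails over sections 4 and 10.3.2, and that standard-care control scans are not brought into the endpoint.

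A reader might take this as a threat to the trial's main result. It is not. LSG is one of four exploratory objectives; the primary and secondary endpoints and the sample size are untouched.

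**What to change.** Reconcile the section 9 footnote with section 4 (Post-op list and T5), section 4.1, and sections 10.3.2.4 and 10.3.2.5, in one of three ways:

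1. Delete the footnote, so that both arms have the T5 scan.
2. Keep the research label, but state that the 12-month scan already listed in section 4 is collected for controls at the T5 timing, after the same ten days without compression, and read masked together with the BioBridge scans.
3. Keep the footnote as a true restriction, declare LSG a within-BioBridge description that supports no conclusion about the device against VLNT alone, and drop the blinding statement in 10.3.2.5.

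Section 12.5.2 needs no edit under option 3 on account of comparative wording, since its LSG paragraph has none. Under options 1 and 2, adding relative-to-control wording to 10.3.2 would make the intended comparison explicit.

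The cost is mainly editorial. Controls already attend T5, and section 4 already allows one scan to serve both purposes. Options 1 and 2 do require control scans to be timed to T5. Where such a scan would not otherwise be done as standard care, it carries radiation exposure; section 4.1 puts the additional research exposure at about 7 mSv without saying whether that is per scan or for both time points. Option 3 adds no procedures but gives up the comparison.

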10. MEASUREMENTS

Primary and Secondary Assessments

For each analysis undertaken, primary and secondary, participants will be randomized into one of two groups: VLNT (control arm) or VLNT-BioBridge (intervention arm). Change in intervention group compared to control group will be evaluated.

10.1 Primary Outcome

To determine whether the addition of the BioBridge scaffold to vascularized lymph node transfer will improve the outcome of surgical treatment of secondary arm lymphedema resulting from treatment of breast cancer. Primary endpoint is % change in (excess) limb volume, from baseline to Month 12, in the intervention group relative to control group. Dispersion (variance) will be assessed as the standard deviation.

The single subject enrolled to this study prior to the December 2019 revision will not be included in the primary outcome analysis nor the final analysis, due to the significant changes in the study.

10.1.1 Relevant Subset

Target population, for both groups, are participants with unilateral upper extremity lymphedema, secondary to breast cancer treatment, who plan to undergo VLNT.

10.1.2 Measurement Definition

Quantitative assessment of limb volume (mL) of the affected limb at study end (Month 12) will be compared to pre-intervention (baseline) value. Baseline value is defined as the arithmetic mean of measurements obtained at the two qualifying screening visits. Mean difference in limb volume in the intervention group relative to control group at study end (Month 12) following surgical intervention will be evaluated.

10.1.3 Measurement Methods

Limb volume quantification, of affected and non-affected limbs, will be performed using circumferential measurements of the limb, at 4 cm intervals beginning at the wrist. The limb volume will be determined using a truncated cone formula{volume = $\pi h(R^2 + Rr + r^2)/3$, let h be the height, R the radius of the lower base, and r the radius of the upper]. Limb circumference, for calculation of limb volumes, will be serially measured at screening evaluations and in follow-up to study end (Month 12). For quantitative analysis, the volume of the ipsilateral arm will be expressed as a percentage of the unaffected arm volume and of the pre-treatment volume of the ipsilateral arm.

10.1.4 Measurement Time Points

Limb circumference, for calculation of limb volumes, will be measured at screening evaluations to scheduled follow-up visits (Month 3, 6, 9, 12). The primary endpoint will be assessed at time point, 12 months.

10.1.5 Response Review

Results will be evaluated by a designated, independent, blinded reviewer.

10.2 Secondary Outcome

Change in measurement of dermal thickness, as measured by caliper skin fold thickness, from

baseline to Month 12, in the intervention group relative to control group.

10.2.1 Relevant subset

The target population are participants with unilateral upper extremity lymphedema, secondary to breast cancer treatment, who plan to undergo VLNT.

10.2.2. Measurement Definition

Measurement of dermal thickness at study end (Month 12) will be compared to pre-intervention (baseline) value. Baseline value is defined as the arithmetic mean of values (with standard deviation) obtained at the two qualifying screening visits. Mean difference in dermal thickness measurement in the intervention group relative to control group at study end (Month 12) following surgical intervention will be evaluated. Dispersion (variance) will be assessed as the standard deviation.

10.2.3 Measurement Methods

Skin thickness measurements (in mm) will be performed with a Lange skinfold caliper (Beta Technology, Santa Cruz, CA). For each participant, at each assessment, 3 measurements will be obtained: the dorsum of the hand, the midpoint of the volar aspect of the forearm, and the midpoint of the medial aspect of the upper arm. At the initial evaluation, a dermatographic pencil is used to mark the site of each measurement. Once the locations are determined, the location is noted (measured from the wrist). These locations will be re-utilized for serial measurements for each follow-up visit. Calipers are calibrated prior to each use. Assessor will be blinded to treatment status. Pre and post-surgical aggregate scores of lymphedema-affected limb will be utilized and reported.

10.2.4 Measurement Time Points

Skin thickness measurements will be performed at screening evaluations to scheduled follow-up visits (Month 3, 6, 9, 12).

10.2.5 Response Review

Results will be evaluated by a designated, independent, blinded reviewer.

10.3 Exploratory Objectives and Endpoints

Exploratory Outcomes have not been defined for ClinicalTrials.gov.

10.3.1 Change in lymphedema Quality of Life (LymQOL)

Change in lymphedema Quality of Life (LymQOL) aggregate score, from screening evaluations to scheduled follow-up visits (Month 3, 6, 9, 12).

